4.6 Child health-related quality of life instrument

All instruments will be scored as described in the referenced publications. The Impact on Activities and Routines Instrument, used to measure child health-related quality of life, has not been published yet. For this reason, we describe this instrument and its scoring here. The Impact on Activities and Routines Instrument has the option of using a child-reported question or a parent-reported question. The child-reported question will be utilized, unless the participant is too young to self-report or prefers parent report. The child reported question is: In the past 7 days, how much did the medical concern that led to your hospitalization impact your usual activities or routines (e.g., go to school, play, eat, sleep)? The parent-reported questions that will be used, if necessary, is: In the past 7 days, how much did the medical concern that led to your child's hospitalization impact their usual activities or routines (e.g., go to school, play, eat, sleep)? Answer choices to both questions are: 1, Not at all | 2, Slightly | 3, Moderately | 4, Quite a lot | 5, Extremely. Mean score responses will be used in analyses.

5 Overall Study Design

FAAN-C is a multicenter RCT that will enroll 2,674 patients across approximately 10 hospitals, including children's and community hospitals. Inclusion of community hospitals is a priority because community hospitals care for the majority of hospitalized children in the US¹⁷ but are historically underrepresented in research.^{60, 61} FAAN-C is powered for non-inferiority of a recommendation for PRN follow-up compared to a recommendation for automatic follow-up, with 14-day all-cause

^bUrogenital imaging for urinary tract infections will be excluded from this measure because urogenital imaging is often recommended by guidelines and the potential benefits of such imaging have a longer time horizon than the present study.

hospital readmission as the primary outcome. Non-inferiority trials test the hypothesis that one intervention is not worse than a comparator with respect to the primary outcome. This design is useful when evaluating an intervention that is more efficient, less prone to adverse events, and/or less costly than the accepted comparator.⁶² If non-inferiority is demonstrated, patients can benefit from a simpler, safer alternative intervention. In the case of FAAN-C, there are clear advantages to PRN follow-up over automatic follow-up. Namely, a recommendation for PRN follow-up affords families the convenience of not necessarily having to attend another medical appointment, which means decreased costs and decreased time away from work and school. As such, FAAN-C fits a non-inferiority trial design. If PRN follow-up is shown to be non-inferior to automatic follow-up for the primary outcome (and safety outcomes are similar), the convenience and cost advantages of PRN follow-up are manifest enough that PRN follow-up would generally be preferred to automatic follow-up.

6 Study Population

Table 6 details the inclusion and exclusion criteria for participants in FAAN-C. Eligible participants must meet all inclusion criteria and none of the exclusion criteria.

Table 6: Study Population

	Inclusion	n Criteria	Exclusion Criteria			
Pneumonia	- Age <18 years - Hospitalized (including observation visits) - Parent speaks English or Spanish	- Attending diagnosis of pneumonia as the principal disease that led to hospital admission	- Presence of a comorbid disease that is both chronic and complex* - principal disease required surgical intervention (beyond superficial incision and drainage)	– Received a chest tube		
Urinary Tract Infection		- Attending diagnosis of urinary tract infection as the principal disease that led to hospital admission	- Immunodeficiency (innate or receiving a long-term immunosuppressive medication) - A well-child check-up or post-hospitalization follow-up visit is already scheduled within 7 days of hospital discharge	- History of neurogenic bladder or urologic surgery (beyond circumcision) - Renal imaging anticipated within 7 days of hospital discharge - Complicated by a renal abscess		
Skin and soft tissue infection		- Attending diagnosis of skin and soft tissue infection as the principal disease that led to hospital admission	 Parent or participant strongly prefers PRN or automatic follow-up A medical provider feels strongly that a post-hospitalization follow-up visit is needed within 7 days of hospital discharge 	- Chronic wound - Postoperative infection - Predisposition to poor wound healing - Discharging with a drain in place - Complicated by necrotizing fasciitis or toxic shock syndrome		
Acute Gastroenteritis		- Attending diagnosis of acute gastroenteritis as the principal disease that led to hospital admission	Sibling concurrently hospitalized Unable to identify a clinic where the participant would receive any needed post-hospitalization follow-up	- Complicated by hemolytic uremic syndrome		

^{*}Definition of comorbid disease that is both chronic and complex: Any disease that can be reasonably expected to last at least 12 months (unless death intervenes) and to involve either several different organ systems or 1 organ system severely enough to require specialty pediatric care and probably some period of hospitalization in a tertiary care center⁶³

6.1 Treatment of Subjects

At the time of hospital discharge, families will be randomly assigned to either PRN or automatic follow-up recommendations as described below:

PRN follow-up: "You do not need to schedule a follow-up visit with your child's regular doctor today. If your child's illness continues to improve, you do not need to have a visit with your child's regular doctor within the next 7 days. If your child's illness does not seem to be getting better or you develop any new concerns, we recommend that you contact your child's regular doctor to discuss whether a follow-up visit might be necessary."

Automatic follow-up: "Please schedule a follow-up visit with your child's regular doctor before leaving the hospital. Please schedule the visit to occur within the next 7 days and plan to attend the visit even if your child's illness is getting better."

The automatic follow-up instructions are aligned with proposed quality metrics⁴⁰ and previous studies of automatic follow-up.^{25, 26, 28, 32, 34} Both the PRN and automatic follow-up instructions were utilized successfully for our prior trial, BeneFIT.²³

Pragmatic features of comparators. Pragmatic features that will make findings from FAAN-C more generalizable and quickly scalable include the following: 1) Follow-up visits, whether automatic or deemed necessary in the PRN group, can be conducted either in-person or via telehealth. The decision about whether a visit should occur in person or via telehealth will be at the discretion of families and their medical providers. 2) Beyond randomization to either PRN or automatic post-hospitalization follow-up recommendations, FAAN-C is not otherwise prescriptive for a participant's medical care. Hospitalists have complete autonomy about the patient's care while hospitalized, and PCPs have complete autonomy for the patient's care after hospitalization. 3) Beyond embedding follow-up instructions in the electronic health record, the discharge process is otherwise preserved according to each hospital's usual procedures.

7 Treatment Assignment Procedures

7.1 Randomization

Randomization will be performed using randomly permuted blocks of random sizes, stratified by the four types of infection and hospital site. Children will be assigned in a 1:1 ratio to receive a recommendation for either PRN or automatic post-hospitalization follow-up. Randomization sequence generation will be performed by study investigators who are not involved in the intervention assignment of enrolled participants. Allocation concealment will be maintained by a central, automated computer platform (REDCap).

7.2 Blinding

Owing to the nature of the comparators, blinding of participants and their medical providers is not possible. However, outcomes that require adjudication will be adjudicated by persons blinded to the subject's randomized group. Outcomes requiring adjudication in FAAN-C are the safety outcomes (hospital readmissions related to the index infection and medical errors). Specifically, a clinician will determine if the readmission was related to the index infection and a separate clinician will score parent-reported medical errors in terms of severity (as described in the Safety Reporting section of this protocol). The clinicians performing adjudication of these outcomes will be blinded to the subject's randomized group.

8 Study Procedures

8.1 Study Schedule

A schedule of study events for each participant is outlined in Table 7. "While hospitalized" events will occur between the time of hospital admission and the time of hospital discharge.

Page 22 of 44 Protocol 1.00 ([name])

Table 7: Study Schedule

	While hos- pitalized	After hospital discharge			
		Day 7	Day 14	Day 30	Day 180
Screening	/				
Informed consent	/				
Parent interview	/				
Randomization	/				
Notify family, PCP, and inpatient team of assignment	/				
Chart review				/	
Process measure					 
Completion of a post-hospitalization follow-up		×			
Outcomes					
All-cause hospital readmissions		0	×	0	
Medical interventions		0	×	0	
Child health-related quality of life	0	×	0	0	
Cost burden		0	×	0	
Child time		0	×	0	
Parent time		0	×	0	
Symptom duration	0	×	0	0	
Total additional ambulatory visits		0	0	×	
Non-primary care ambulatory visits		0	0	×	
Parent self-efficacy	0	×		0	0
Parent anxiety	0	×		0	
Satisfaction with care	0	×			
Telephone or electronic communications with medical providers		0	×	0	
Well-child visits	0				×
Immunizations	0				×
Usual place of medical care	0				×
Medical interventions related to the index infection		0	×	0	
Medical errors		0	×	0	
Hospital readmissions related to the index infection		0	×	0	

^{/ =} task performed at the specified timepoint

^{○ =} measured at the specified timepoint

X = measured at the specified timepoint and this is the timepoint used for primary analyses

8.2 Screening and Informed Consent

Study staff will regularly review the list of hospitalized patients at their site. Study staff will verify eligibility by a combination of reviewing the subject's medical record and discussion with the inpatient team caring for the patient, as necessary. After study eligibility has been verified, study staff will approach the parents of the eligible child for consent (and assent from the child, as appropriate). Parents who consent to study participation will then be asked to participate in the parent interview. Within REDCap, a record will be kept of all screened but not enrolled participants. Reasons for not enrolling will be recorded.

8.3 The Parent Interview

The parent interview will obtain sociodemographic data (e.g., race, ethnicity, financial hardship) about the child and the child's parents. Baseline measurements of the outcomes that are measured during hospitalization will also be measured during the parent interview. Screening, consent, and the parent interview will occur before randomization.

8.4 Randomization Process

Randomization will occur when study staff learn that hospital discharge for the study participant is likely to be that day and/or discharge orders have been placed. Prior to randomization, study staff will complete an enrollment checklist in REDCap. The enrollment checklist will verify that all necessary pre-randomization items have been completed. When the enrollment checklist is complete, REDCap will supply the study staff with the patient's randomization assignment. Study staff will notify the patient and their parents of their randomization assignment and their recommended follow-up strategy (PRN or automatic follow-up). Study staff will also communicate the participant's randomization assignment to the participant's inpatient medical team and PCP.

8.5 Chart Review

Study staff will perform chart review. We will collect data elements related to each child's past medical history (e.g., comorbidities), as well as the complexity and severity of their acute infection while hospitalized (e.g., presence of bacteremia, need for intensive care). Chart reviewers will also record readmissions. For each readmission, data elements for the severity and complexity of the illness(es) for which the participant was readmitted will be collected. Chart review can begin anytime after a participant is discharged from the hospital but cannot be completed until the participant is at least 30 days out from discharge.

8.6 Outcome Measurement

Outcomes will be measured according to the timing in Table 7. "While hospitalized" outcomes will be measured prior to randomization. "After hospital discharge" outcomes will be measured by surveying parents on days 7, 14, 30, and 180, as specified. An additional 4 days will be permitted for the collection of data on the 7, 14, and 30 day timepoints and \pm 7 days for the day 180 timepoint. For example, day 7 outcomes can be collected between day 7 and day 11. These intervals allow for holidays, weekends, and other reasons for parent unavailability that may preclude contact on the exact day.

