Automatic follow-up for previously healthy children recovering from common infections may not be necessary While the rationale for automatic follow-up is compelling for children who have chronic and complex medical needs, most hospitalized children are previously healthy and hospitalized for acute conditions from which complete recovery is expected. ^{16, 17} Five of the top 10 reasons for pediatric hospitalization are acute infections, including: pneumonia, bronchiolitis, skin and soft tissue infections, gastrointestinal infections, and urinary tract infections. ¹⁸ Together, these infections are responsible for over 500,000 pediatric hospitalizations each year in the US. ¹⁸ After hospital discharge, the vast majority of previously healthy children recover from these infections within a matter of days and rarely experience an interim worsening of their illness (readmission rates are <5% ¹⁰). Given such a reassuring prognosis, the benefit of automatic follow-up for previously healthy children recovering from common infections is unclear.

PRN follow-up is a patient and family-centered alternative to automatic follow-up Patient and family-centered care means that patient and family values guide all clinical decisions. Patients and families whose preferences are incorporated into their plan of care make more value-congruent choices and are more likely to follow the plan of care. A PRN (*pro re nata*, "as-needed") follow-up strategy is aligned with the principles of patient and family-centered care, encouraging families to monitor their child's symptoms after hospital discharge and schedule a visit if the child does not improve or if new concerns arise. As such, PRN follow-up empowers families with greater autonomy and allows them to consider their preferences and values when deciding whether or not to pursue post-hospitalization follow-up. Taking this decision-making away from families runs the risk of undermining their sense of self-efficacy—a patient's or parent's confidence to solve self-identified problems. Despite being patient and family-centered, PRN follow-up is prescribed to a minority of patients (10–15%) largely because of limited evidence. PRN follow-up

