4.5 Safety Outcomes

Safety outcomes are also listed in Table 5. Safety outcomes were selected with the goal of capturing adverse consequences (beyond hospital readmission, the primary outcome) that families might experience as a result of a recommendation for PRN follow-up, compared to a recommendation for automatic follow-up. A recommendation for PRN follow-up may result in those participants having to attend a greater number of other types of ambulatory visits (e.g., emergency department visits). The subset of non-primary care ambulatory visits will be measured because these visits have the potential to be more burdensome for participants (i.e., larger co-pays and urgent, less convenient visits), relative to a primary care visit. It is also possible that a recommendation for PRN follow-up could result in greater exposure to medical errors after hospital discharge (e.g., medication problems, complications of care), since another medical provider may not connect with the child and family shortly after hospital discharge. In addition to the primary outcome of all-cause hospital readmission, an additional safety outcome will be hospital readmissions related to the index infection. All safety outcomes are measured by parent report, from the time of hospital discharge

until the specified time after discharge.

Table 5: Secondary, exploratory, and safety outcomes

Outcome	Definition	Expected outcomes type for analysis ^a
	Secondary outcomes	
Medical interventions	Proportion of participants who receive either a laboratory test, imaging test ^b , or a new medication within 14 days of hospital discharge	Binary
Child health-related quality of life	Mean health-related quality of life score 7 days after hospital discharge, measured by the Impact on Activities and Routines instrument	Normal
	Exploratory outcomes	
Cost burden	Mean total costs to parents (missed income and expenses) related to the participant's illness within 14 days of hospital discharge, measured by the cost burden survey in Chang et al ⁴⁹	Binomial- Gamma hurdle
Child time	Mean number of hours of school or daycare missed by the participant within 14 days of hospital discharge as a result of their medical needs	Over-dispersed Binomial
Parent time	Mean number of hours spent away from responsibilities (work or non-work related) by parents within 14 days of hospital discharge as a result of their child's medical needs	Normal or Gamma

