Symptom duration	Proportion of participants who have completely recovered from their infection at 7 days after hospital discharge	Binary
Total additional ambulatory visits	Mean number of ambulatory visits (in-person or via telehealth) that a participant attends, apart from the post-hospitalization follow-up visit, within 30 days of hospital discharge; Ambulatory visits include clinic, urgent care, and emergency department (not resulting in hospital admission) visits.	Negative Binomial
Non-primary care ambulatory visits	Mean number of ambulatory visits (in-person or via telehealth) to non-primary care providers, within 30 days of hospital discharge; Non-primary care providers will include all providers outside of the clinic that families identify as their primary care clinic.	Negative Binomial
Parent self-efficacy	Mean self-efficacy score 7 days after hospital discharge, measured by the PROMIS self-efficacy short form ⁵⁸	Normal
Parent anxiety	Mean anxiety score 7 days after hospital discharge, measured by the PROMIS anxiety short form ⁵⁸	Normal or Gamma
Satisfaction with care	Proportion of participants who report agreeing or strongly agreeing with the statement, "I am satisfied with the medical care my child has received since hospital discharge," 7 days after hospital discharge	Binary
Telephone and electronic communications with medical providers	Mean number of telephone and electronic (excluding telehealth visits) communications with a medical provider within 14 days of hospital discharge	Negative Binomial
Well-child visits	Proportion of participants who attend a well-child visit within 6 months of hospital discharge	Binary
Immunizations	Proportion of participants who receive an immunization within 6 months of hospital discharge	Binary

Usual place of medical care	Proportion of participants who report having a usual place of medical care 6 months after hospital discharge	Binary	
Medical interventions related to the index infection	Proportion of participants who receive either a laboratory test, imaging ^b test, or a new medication related to the index infection within 14 days of hospital discharge	Binary	
Safety outcomes			
Medical errors	Proportion of parents who report that their child experienced a medical error within 14 days of hospital discharge, measured by the Family Safety Interview ⁵⁹	Binary	

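### The day-7 quality-of-life item looks back from the day of contact, so answers on days 8 to 11 describe a later week, and the 6-month survey may open at day 173, before its period has ended

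*Protocol*

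**What the plan says.** **Windows (8.6).** For the early surveys, "An additional 4 days will be permitted for the collection of data on the 7, 14, and 30 day timepoints". The protocol gives its own example: "day 7 outcomes can be collected between day 7 and day 11". The last survey has a two-sided window, plus or minus "7 days for the day 180 timepoint".

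**Quality of life.** Table 5 defines this main secondary outcome as "Mean health-related quality of life score 7 days after hospital discharge". Section 4.6 gives the child's question: "In the past 7 days, how much did the medical concern that led to your hospitalization impact your usual activities or routines". The parent version has the same look-back period. Section 9.2 tests this outcome formally under Bonferroni-Holm. The analysis of covariance in 9.4 adjusts for baseline score, infection type and site.

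**Other day-7 items.** The satisfaction statement in Table 5 covers care from discharge up to the moment of answering. Recovery is defined as "Proportion of participants who have completely recovered from their infection at 7 days after hospital discharge", but the survey wording is not given.

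**Six-month outcomes.** Table 5 defines one as "Proportion of participants who attend a well-child visit within 6 months of hospital discharge". Immunizations are defined over the same period.

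**The concern.** The quality-of-life definition names a fixed time after discharge, but the question is anchored to the day the family is reached. The window therefore decides which week is measured. This matters because the protocol expects that "the vast majority of previously healthy children recover from these infections within a matter of days", so a week that starts on day 4 should on average be a better week than one that starts at discharge. It is also in the first seven days that the arms are meant to differ: 6.1 asks the automatic arm to attend a visit in that period, and 3.3 measures attendance over it. Late answers replace part of that period with later days.

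For well-child visits and immunizations the difficulty is different. The survey may be taken before the counting period is over, and an early survey cannot report what has not yet happened. Section 4.4 anticipates only small decreases in these outcomes under PRN follow-up, so a small systematic undercount is worth avoiding.

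**Working it through.** **1. Windows (inputs from 8.6).** 7 + 4 = 11, which matches the protocol's own example. Likewise 14 + 4 = 18 and 30 + 4 = 34. For the last survey, 180 − 7 = 173 and 180 + 7 = 187. It is the only window that opens early.

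**2. Overlap of the quality-of-life look-back with the first week.** An answer on day *t* covers days *t* − 7 to *t*. The overlap with days 0 to 7 is 7 − (*t* − 7) = 14 − *t* days.

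| Day answered | Days covered | Days shared with first week | Share |
|---|---|---|---|
| 7 | 0–7 | 7 of 7 | 100% |
| 8 | 1–8 | 6 of 7 | 86% |
| 9 | 2–9 | 5 of 7 | 71% |
| 10 | 3–10 | 4 of 7 | 57% |
| 11 | 4–11 | 3 of 7 | 43% |

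The protocol does not say how contacts will spread over the window. If they spread evenly over the five days (an assumption), the mean overlap is (7 + 6 + 5 + 4 + 3)/5 = 5 of 7 days. The extremes are 7 of 7 if all answer on day 7 and 3 of 7 if all answer on day 11. No size in score units can be given, because the protocol reports no course of this score over time.

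**3. Recovery, only if it is asked as status at contact.** Assume exponential time to recovery with mean *m*. The protocol gives no figure for the four enrolled infections, so *m* is varied from 3 to 10 days. The proportion recovered by day *t* is 1 − exp(−*t*/*m*).

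| Mean (days) | By day 7 | By day 11 | Shift (points) |
|---|---|---|---|
| 3 | 90.3% | 97.4% | 7.1 |
| 5 | 75.3% | 88.9% | 13.6 |
| 7 | 63.2% | 79.2% | 16.0 |
| 10 | 50.3% | 66.7% | 16.4 |

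This compares everyone asked on day 7 with everyone asked on day 11. It is not a difference between arms. An arm difference equals the imbalance in day-11 contacts times the shift. A 10-point imbalance gives 0.10 × 7.1 to 0.10 × 16.4, or about 0.7 to 1.6 points. A 20-point imbalance gives about 1.4 to 3.3. Both imbalances are hypothetical.

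**4. Six-month outcomes.** Half a year is 365.25/2 = 182.6 days. Day 173 falls 7 days before day 180 (7/180 = 3.9%) and 9.6 days before six calendar months (9.6/182.6 = 5.3%). With a constant rate and a true 6-month proportion *p*, the proportion seen by day 173 is 1 − (1 − *p*)^(173/182.625).

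| True *p* | Seen by day 173 | Missed (points) |
|---|---|---|
| 30% | 28.7% | 1.3 |
| 50% | 48.1% | 1.9 |
| 70% | 68.0% | 2.0 |
| 90% | 88.7% | 1.3 |

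These are upper figures, since they take every survey to be on day 173.

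**The case against.** A four-day allowance for reaching families is ordinary, is explained in 8.6 and applies to both arms alike. Answers given on day 7 are unaffected. Table 5 fixes when the score is taken and does not say that it must cover exactly days 0 to 7. Handling of contact day may be settled in the statistical analysis plan, which is not at hand. All of this stands, and it limits the point to late answers and to blurring. It does not remove the fact that the protocol's own item wording lets the measured week move by up to four days.

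Four stronger readings are tempting, and the protocol does not support them.

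- A reader might infer a biased comparison, because families are unblinded. That needs contact timing to differ by arm. Nothing in the protocol suggests it, and the retention measures in 8.7 are the same for both arms.
- A reader might take the mean time to symptom resolution in BeneFIT (10 to 11 days) and claim a 16-point error in recovery. That trial enrolled bronchiolitis, which is not one of the four infections here. Recovery is an exploratory outcome, and its item may be dated: 9.5 plans a log-rank test and Cox model of symptom duration, which need a recovery time. If dates are collected, day-7 status can be derived.
- A reader might extend the fast-recovery argument to the 6-month outcomes. It does not apply to well-child visits or immunizations.
- A reader might assume that days not observed before six months are scored as no event. The protocol does not say so. Section 14.1 lists visit dates among the data collected, so late reports can be cut back to six months, but an early survey cannot be extended. For having a usual place of care, which is a status at one time, a two-sided window is unobjectionable.

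**Conclusion.** The point holds in limited form and is worth correcting. For a formally tested secondary outcome, answers on days 8 to 11 describe a week that shares only 6 to 3 of its 7 days with the first week after discharge. Day of contact is not among the covariates listed in 9.4. The satisfaction item drifts in the same way. The expected consequence is added noise and possible dilution of a first-week difference. Its size in score units cannot be computed from the protocol and depends on how many families answer late.

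For well-child visits and immunizations, opening the survey at day 173 costs about 1 to 2 percentage points at most, assuming a constant rate and true proportions of 30% to 90%. Both arms are exposed to the same undercount.

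The primary outcome is largely protected: readmissions are asked about again at day 30 (4.2), and chart review cannot close before day 30 (8.5).

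**What to change.** - **Day-7 items.** Keep the four extra days for reaching parents. Anchor the quality-of-life question to the first seven days after discharge, with the dates filled in for each family. Anchor the recovery and satisfaction items to the same end date, or collect the date of recovery.
- **Minimum alternative.** Leave the wording as it is, record the day of contact, and pre-specify a sensitivity analysis on it for the quality-of-life score.
- **Six-month outcomes.** For well-child visits and immunizations, open the survey only once six months have passed, and count events by date.

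**Cost.** No extra contacts are needed. Late responders recall a week that ended up to four days earlier. The day-7 wording would differ slightly from the baseline, day-14 and day-30 administrations, which matters a little because the baseline score is the covariate in 9.4. Section 4.6 says the instrument is not yet published, so the protocol cites no published scoring standard that the change would break. The change to the 6-month window has almost no downside.
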